4.1 Informed Consent

Prior to enrollment, all patients will be informed in detail about the nature of the clinical investigation, as well as its risks, potential benefits, and any anticipated discomforts. All patients must provide written informed consent using Ethics Committee (EC) approved informed consent document.

Proper informed consent should be obtained in accordance with local/country guidelines as needed.

4.2 Screening Evaluation

All patients considered for enrollment must undergo a thorough screening evaluation prior to the scheduled treatment with the everlinQ System. The screening evaluation includes:

- Collection of demographic data;
- A medical history and physical exam;

- A laboratory evaluation (i.e. blood tests); and
- A duplex ultrasound and optional angiography/venography assessment.

There will be a final assessment of the suitability of the patient's study eligibility due to vascular anatomy or other criteria made at the time of the index procedure and thus, there may be some consented subjects who are determined to be ineligible who will not be enrolled in the study.

4.2.1 Duplex Ultrasound

A duplex ultrasound assessment needs to be performed of the flow rates and inner diameters of the arteries and veins of the target vessels based on the training requirements provided for the study.

4.2.2 Angiography/Venography

An optional angiographic or venographic assessment of the suitability of the arteries or veins intended for the endoAVF.

4.3 Index Procedure

If a patient presents for the index procedure with an active localized infection, or other medical condition that precludes treatment at this time, the procedure should be delayed until the infection or medical condition is treated and resolved.

If the Investigator is not an experienced user of the everlinQ System, a Sponsor's representative will be present as needed for procedures at each site to provide technical guidance to the Investigator.

4.4 Follow-Up Visits

See **Table 1** for required and optional follow-up visits.

4.4.1 Unscheduled Visit

In addition to scheduled follow-up visits, the patient should be instructed to contact the Investigator at any time during the follow-up period if he/she has questions or concerns relating to the procedure or the endoAVF. If the patient returns to the clinic for evaluation related to his/her participation in the study, an Unscheduled Visit evaluation should be performed and this data should be recorded on the Follow-Up Visit Case Report Form.

4.4.2 Patient Disposition

The Patient Disposition Case Report Form should be completed whenever a patient exits the study. This includes patients enrolled in the study who:

- complete the study protocol,
- withdraw from the study,
- are lost to follow-up,
- are deceased,
- have other reason(s) for exiting the study.

4.5

Adverse Events

For the purpose of this protocol, an AE will be defined as any adverse medical change (i.e., *de novo* or increased severity in a preexisting condition) from the subject's baseline condition that occurs during the course of the clinical study, after starting treatment, whether considered treatment-related or not. "Treatment" includes all investigative or commercially-approved products administered according to the Study Protocol.

Any pre-planned procedures, interventions, etc. or expected progression of pre-existing conditions (e.g., cancer progression) will not be considered AEs for this study. In addition, normally expected symptoms caused by the treatment are not considered an AE for this study. These may include but are not limited to:

- Transient arterial spasm resolving spontaneously OR with medication only.
- Minor discomfort or bruise at the arterial access place.
- Small amount of bleeding at point of arterial access.
- Transient numbness, tingling or coolness that resolved within 4 weeks post index procedure.
- Bruising at the AVF creation site.
- Side effects of standard-of-care medications.
- Hematoma at the arterial and/or venous access site(s) managed prior to patient discharge and did not adversely affect patient discharge.

Only AEs that are relevant to index procedure, study device, access site or AVF will be collected in the study. For example, if the patient has knee replacement or undergo hysterectomy, these events will be considered as non-study related and will not be required to be recorded via Adverse Event form.

AE Type	Definition
Serious Adverse Event (SAE)	AE that 
a) led to death,b) led to serious deterioration in the health of the subject, that either resulted in
1) a life-threatening illness or injury, or2) a permanent impairment of a body structure or a body function, or3) in-patient or prolonged hospitalization, or4) medical or surgical intervention to prevent life-threatening illness or injury or permanent impairment to a body structure or a body function,c) led to foetal distress, foetal death or a congenital abnormality or birth defect 
NOTE: Planned hospitalization for a pre-existing condition, or a procedure required by the Study Protocol, without serious deterioration in health, is not considered a SAE.¹³

Adverse Device Effect (ADE)	AE related to the use of study device. NOTE: This definition includes adverse events resulting from insufficient or inadequate IFU, deployment, installation, or operation, or any malfunction of the study device. This definition includes any event resulting from use error or from intentional misuse of the study device.
Serious ADE (SADE)	ADE that has resulted in any of the consequences characteristic of a SAE
Unanticipated SADE (USADE)	USADE which by its nature, incidence, severity or outcome has not been identified in the current version of the study protocol, IFU, or other study documentation.
SUSAR	A SUSAR is suspected unexpected serious adverse reaction
Anticipated SADE (ASADE)	An effect which by its nature, incidence, severity or outcome has been identified in the study documentation.

To classify the event, you may follow the steps below (please refer to additional local requirements as needed).

Is this event:					
1. Serious	Yes		No		
2. Study device or procedure related	Yes		No	Yes	No
3. Unanticipated?	Yes	No			
Event type is →	USADE or SUSAR	ASADE	SAE	ADE	AE (i.e., non- SAE)

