2.2 Risks

Many of the potential risks and complications associated with the everlinQ System and procedure are similar to the risks expected for CKD patients undergoing surgically created arteriovenous fistula (AVF) procedures. The potential risks related to the everlinQ System and procedure are similar to surgical AVF creation and may include but not limited to:

- Bruising
- Numbness, tingling and/or coolness in the fistula extremity
- Occlusion/stenosis (AVF clots)
- Thrombosis (AVF completely clotted and cannot be used)
- Failure to mature (AVF can never be used)
- Additional procedures (interventions)
- Venous hypertension (arm swelling)
- Aborted or longer procedure
- Swelling, irritation or pain
- Bleeding, hematoma (a solid swelling of clotted blood within the tissues) or hemorrhage (an escape of blood from a ruptured blood vessel)
- Wound problem
- Fever (pyrogenic reaction)
- Steal or ischemia (not enough blood flow to hand)
- Embolism (blood clot or device piece)
- Infection (local or in the blood (bacteremia))
- Increased risk of congestive heart failure (heart fails due to increased flow from AVF)
- Vessel, nerve or AVF damage or rupture
- Pseudoaneurysm (leaking hole in artery that forms blood clot on outside of it)
- Heart problems such as arrhythmias (abnormal beats) that can be caused due to high levels of potassium in the blood (mostly due to CKD and not the TVA device or procedure)
- Death (mostly due to CKD related complications not the TVA device or procedure)
- Burns
- Problem due to sedation or anesthesia
- Sepsis (systemic inflammatory reaction)
- Toxic or allergic reaction
- Electrocution

In addition, fistula infiltration injury due to needle cannulation of the fistula is also a known risk/event.

Most of these potential risks also exist for creation of standard (surgical) AVFs. There may also be other risks related to use of the everlinQ System and procedure that are not listed or that are not known at this time. This study will help characterize the adverse events associated with the everlinQ System.

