3 STUDY METHODOLOGY

3.1 Study Design

This is a prospective, single-center study to evaluate the everlinQ System when used to create an endoAVF in hemodialysis patients. A total of up to 50 subjects will be enrolled and will undergo an endoAVF creation procedure using the everlinQ System. All subjects will be followed for up to 12 months post index procedure based on Investigator's discretion.

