3.3 Study Endpoints

Study endpoints will be summarized using descriptive statistics. There are no formal hypothesis tests associated with these endpoints.

- **Technical success:** Verification that an endoAVF has been created and remains patent 1-7 Days after the index procedure. Patency will be determined by experienced examiner as the presence of a bruit that is detected with stethoscope, or presence of thrill, or via Duplex Ultrasound, or via angiogram.
- **Fistula Maturation:** defined as endoAVF that is free of stenosis or thrombosis, with brachial artery flow of at least 500 ml/min and at least 4 mm vein diameter (as measured by duplex ultrasound) OR patient was dialyzed using 2 needles.
- **The Time to Fistula Maturation:** the number of days between the date of AVF creation and the date of endoAVF maturation (based on primary efficacy endpoint definition of maturation).
- **Duration of Central Venous Catheter Exposure:** The rate of CVC use per enrolled subjects at 30-45 Days and other follow-up visits. The analysis will be performed for pre-dialysis and on dialysis patients, as applicable.
- **EndoAVF-related Re-intervention Rate:** The re-intervention rate for endoAVF (defined as any intervention required to maintain or re-establish patency) will be calculated at each available follow-up visit post index procedure.
- **Primary Patency:** The primary patency rate will be determined via Kaplan-Meier methods and based on the time of endoAVF creation until any intervention designed to maintain or reestablish patency or endoAVF abandonment.
- **Secondary Patency:** The secondary patency rate will be determined via Kaplan-Meier methods and based on the time of endoAVF creation until access abandonment. Abandonment due to renal transplant receipt will not be included in this endpoint assessment.
- **Safety:** The safety endpoint is the percentage of patients who experience one or more serious device -related adverse events during the first 3 months following AVF creation.

Additional exploratory analysis:

- Rate of serious procedure-related events will be reported at 3 months.
- Rate of serious device-related event rate will be reported at 3 months.
- Rate of device and/or procedure-related infections at 3 months.
- Arterial and arterialized vein flow rates and diameters will be measured via DUS at 30-45 Days and at each available follow-up visit post index procedure.

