6.4 Records and Reports

All records and reports pertaining to this protocol are subject to inspection by regulatory agencies and must be retained for at least two years after the date on which the investigation is terminated or completed or for two years after the date that the records are no longer required for the purpose of supporting an application to regulatory agencies for commercial approval of the therapy/claims, or per local regulations, whichever is later.

6.4.1 **Investigator's Reports**

The investigator is responsible for the preparation and submission of the reports listed below:

Report	Submitted to	Description
Unanticipated Serious Adverse Device Events and Serious Adverse Device Effects	Sponsor & EC	The investigator's report on any unanticipated serious adverse device event (USADE) or serious adverse device effect (S A D E) must be submitted within 10 working days after the investigator first learns of the event.
Withdrawal of EC approval	Sponsor	The investigator must report a withdrawal of reviewing EC approval within 5 working days.
Deviations from Study Protocol	Sponsor & EC	Notification must be made within 5 working days of the occurrence of an emergency deviation (made to protect the life or physical well-being of a subject). If the deviation affects the rights, safety, or welfare of the subjects (and is not an emergency), or the scientific soundness of the investigation, prior approval must be obtained from Sponsor, the reviewing EC and applicable Regulatory Authorities (when required). For all other deviations, prior approval must be obtained from Sponsor. All deviations must be documented on a Protocol Deviation Form.
Failure to obtain Informed Consent Form	Sponsor & EC	Notification must be made within 5 working days of use of the device.

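### Serious events can be screened out as not relevant, or as disease progression, before any AE form or causality grade is required, so that screening step cannot be audited

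*Combined protocol and SAP*

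**What the plan says.** Section 4.5 starts from a broad definition: an AE is any adverse change from baseline that arises "after starting treatment, whether considered treatment-related or not". It then limits collection: "Only AEs that are relevant to index procedure, study device, access site or AVF will be collected in the study". The term relevant is not defined, and there is no exception for serious or fatal events. The two examples of what is left off the AE form are a knee replacement and a hysterectomy, so the filter is not confined to minor complaints. The same section also takes the expected course of pre-existing disease out of the AE definition.

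Section 4.4.2 requires a Patient Disposition form whenever a subject leaves the study, and death is one of the listed reasons. Section 4.5.1 has the investigator grade each AE as definite, probable, unlikely or not related. The safety endpoint in Section 3.3 is the percentage of patients with at least one serious device-related event in the first 3 months.

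On serious device effects, the definitions in Section 4.5 describe an ADE as an "AE related to the use of study device", and a SADE is a serious ADE. The classification table beneath them asks a wider question, "Study device or procedure related", and sends every serious event answered yes to the USADE/SUSAR or ASADE class.

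**The concern.** The safety endpoint depends on a causality judgement, and Section 4.5.1 sets rules for making it. The collection rule puts another judgement in front of that one, without criteria and without a required record. A serious event that fails the first judgement never reaches the second.

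This matters because the protocol's own risk list contains events that are easily put down to underlying disease. Section 2.2 lists "Increased risk of congestive heart failure (heart fails due to increased flow from AVF" among the risks, and it annotates arrhythmia and death as mostly attributable to CKD. A heart failure admission attributed to kidney disease could be missed, although the protocol names heart failure as a risk of the fistula. Section 2.2 also says that some risks may not yet be known and that the study should help to characterize adverse events. A filter based on presumed relevance is weakest for exactly those events.

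**Working it through.** **1. Path of a serious event in the first 3 months**

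| Investigator's view | What the plan requires | Can it be reviewed later? |
|---|---|---|
| Relevant, judged related | AE form and causality grade | Yes |
| Relevant to access site or AVF, judged unrelated | AE form, graded unlikely or not related, classed as SAE | Yes |
| Not relevant, or expected progression; patient survives | No AE form, no grade, no record of the decision | No |
| Not relevant, or expected progression; patient dies | Patient Disposition form only | The fact of death, but no causality grade |

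The gap is confined to the last two rows.

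**2. Entry test against causality test.** Under Section 4.5.1 an event with plausible timing counts as probable, and so as a yes, when device or procedure involvement cannot be ruled out, even if underlying disease is another possible explanation. That is a cautious rule. The relevance screen has no such rule, so an event that 4.5.1 would count as a yes can be stopped before 4.5.1 applies.

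**3. Backstops.** The adverse-event line of the investigator's report table in Section 6.4.1 covers "Unanticipated Serious Adverse Device Events and Serious Adverse Device Effects"; there is no line for SAEs in general. Section 6.10 lets the sponsor request source documents on SAEs, not only related ones, but this helps only if the sponsor learns that the event occurred. No independent adjudication is described.

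**4. Size.** The plan has no figure to reproduce: it gives no event rate and no derivation of the sample size, and "There are no formal hypothesis tests associated with these endpoints". The one numerical input is in Section 3.1: "A total of up to 50 subjects will be enrolled and will undergo an endoAVF creation procedure using the everlinQ System". I assume that all 50 are enrolled and evaluable at 3 months.

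- Change per patient lost from the numerator: 1/50 = 2.0 percentage points. With n subjects it is 100/n; at n = 40, for example, 100/40 = 2.5 points. The patient is lost only if no other qualifying event was recorded for that patient.
- Direction: screening out removes patients from the numerator, never adds them, and leaves the denominator unchanged.
- Exact (Clopper-Pearson) 95% limits: lower = the 0.025 quantile of Beta(x, n − x + 1); upper = the 0.975 quantile of Beta(x + 1, n − x). For x = 0 the upper limit is 1 − 0.025^(1/50) = 0.0711.

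| x/50 | Rate | Exact 95% CI |
|---|---|---|
| 0 | 0% | 0 to 7.11% |
| 1 | 2% | 0.05 to 10.65% |
| 2 | 4% | 0.49 to 13.71% |
| 3 | 6% | 1.25 to 16.55% |

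If two patients truly qualified and both were screened out, the report would show 0% with an upper limit of 7.1% in place of 4% with an upper limit of 13.7%. The count of two is an assumption, and losing both is the worst case for that count.

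**5. SADE wording.** Section 3.3 keeps device-related serious events (the safety endpoint) apart from procedure-related serious events (an exploratory rate). The ADE and SADE definitions follow the device; the classification table merges device and procedure. A count taken from the table's classes would not give the endpoint as stated.

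**The case against.** Targeted collection is a stated choice in a descriptive, single-center study, and a broad AE definition with a narrower collection scope is not in itself a contradiction. Correctly leaving out unrelated events does not change a device-related endpoint. The numerator moves only if a truly device-related serious event is judged not even relevant to the procedure, device, access site or AVF, and nothing in the documents shows how often that would happen. No decision threshold is crossed, because there are no tests. All of this stands and limits the weight of the point.

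Several stronger readings are tempting and should be resisted:

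- A reader might infer that deaths judged unrelated never enter the data. They do, through the Patient Disposition form; what may be missing is an AE form with a causality grade.
- A reader might infer that the unrelated classes will be empty. The filter is relevance, not relatedness, so unrelated access-site and AVF events are still collected. Those classes will be incomplete.
- A reader might infer that a heart failure admission would never be recorded. Its place in the risk list is a reason to treat it as relevant; the documents support only that it could be missed.
- A reader might infer that the safety endpoint as a whole cannot be checked. Recorded events carry a causality grade, and SAE source documents can be requested.
- A reader might take the SADE mismatch as further evidence of under-collection. It is a separate matter: the table brings procedure-related serious events into the device-effect classes and so widens reporting.

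What the objection does not remove is an undefined, unrecorded screen that applies to serious events and can move the endpoint in one direction only.

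**Conclusion.** The point holds in limited form. The plan allows serious events to be set aside as not relevant, or as disease progression, before a form or a causality grade exists, and those events alone cannot be audited from the study record. Any error in that step lowers the safety endpoint, by 2.0 percentage points per patient at 50 subjects and by more if fewer are enrolled. The likely size is unknown, because the documents give no event rate and no information on how often events would be misjudged; the 0/50 and 2/50 figures are for scale only. This does not invalidate the study, but it should be changed: a descriptive safety result rests on complete counts, and the remedy is cheap. The conflict between the SADE definition and the classification table is real and should be reconciled separately.

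**What to change.** Keep the relevance filter for non-serious AEs throughout follow-up. Add to Section 4.5:

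> All serious events, including every death, from the start of the index procedure through 3 months after AVF creation or the 3-month visit, whichever is later, are recorded on the AE form regardless of presumed relevance or attribution to disease progression, and causality is then graded under 4.5.1. After that, serious events relevant to the procedure, device, access site or AVF continue to be recorded to study exit.

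Three parts of this wording are deliberate. The later of the two dates is needed because Table 1 allows the 3-month visit up to 7 days early, which could end full recording before the endpoint window closes. Disease progression is named because an SAE must first be an AE, and the progression exclusion would otherwise still remove the event. The last sentence keeps a rule for the optional 6- and 12-month visits, at which Table 1 also collects AEs.

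Add a matching SAE line to the table in Section 6.4.1. Separately, make the SADE definition and the classification table agree, and record device relatedness and procedure relatedness in distinct fields, so that the safety endpoint and the procedure-related exploratory rate in Section 3.3 are each counted from their own field.

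The cost is protocol wording and extra AE forms for unrelated hospitalizations in at most 50 subjects, mainly over the first 3 months. The same investigator still grades causality, but the events and the grades will be on record for others to review.

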4.5.1 Relationship to Device or Procedure

The investigator will also evaluate the relationship of the adverse event to the everlinQ device or procedure according to the following definitions:

Definite (YES): The AE follows a reasonable timing from treatment (or attempted treatment) with the device and the possibilities of factors other than the device or the index procedure, such as underlying disease, concomitant drugs, or concurrent treatment can be excluded. This includes an AE that occurs during the index (AVF creation) procedure.

Probable (YES): The AE follows a reasonable timing from treatment (or attempted treatment) with the device and the probability of device or procedure involvement cannot be excluded. However, other factors such as underlying disease, concomitant medications, or concurrent treatment may be possible.

Unlikely (NO): The AE follows an unlikely timing relationship from treatment (or attempted treatment) or is more likely due to other factors and there is no definitive information suggesting that it was related to the device or procedure.

Not Related (NO): The AE has no timing relationship from treatment (or attempted treatment) or it can be explained by other factors, including underlying disease, concomitant medication, or concurrent treatment.

The investigator will also evaluate the relationship to the everlinQ portion of the procedure using the yes/no definitions above. The everlinQ portion of the procedure only includes insertion, deployment and removal of the everlinQ catheters.

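### Serious fistula or access-site events are collected, but any scored unrelated to device and procedure enter no planned safety rate

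*Combined protocol and SAP*

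**What the plan says.** On collection, Section 4.5 (Adverse Events) says: "Only AEs that are relevant to index procedure, study device, access site or AVF will be collected in the study".

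On attribution, Section 4.5.1 says: "The investigator will also evaluate the relationship of the adverse event to the everlinQ device or procedure according to the following definitions". Four categories follow. Definite and Probable count as yes; Unlikely and Not Related count as no. A further yes/no question covers part of the procedure: "The everlinQ portion of the procedure only includes insertion, deployment and removal of the everlinQ catheters". The classification grid in Section 4.5 has a single relatedness row, "2. Study device or procedure related", and a serious event answered no there becomes a plain SAE.

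On reporting, the safety endpoint in Section 3.3 is the "percentage of patients who experience one or more serious device -related adverse events during the first 3 months" after fistula creation. The exploratory list adds "Rate of serious procedure-related events will be reported at 3 months", "Rate of serious device-related event rate will be reported at 3 months", and a 3-month rate of infections related to the device and/or the procedure.

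On foreseen harms, Section 2.2 lists steal or ischemia, venous hypertension with arm swelling, and "Increased risk of congestive heart failure (heart fails due to increased flow from AVF"). After the list it names needle infiltration injury of the fistula as a further known event.

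**The concern.** The stated objective (Section 3.2) includes the safety of using the system to create an endovascular fistula. The catheters are removed at the index procedure, and what the patient keeps is the fistula. Events that concern the fistula or the access site are collected, but the protocol defines no attribution for them as such, and every safety result depends on an attribution to something else. A serious event can therefore be on file and absent from all the safety rates.

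This is a single-arm, single-center study with one investigator's site making the relatedness judgements and no comparator against which a pattern of judgement would show. How the safety result reads then depends partly on how that site understands the term procedure-related.

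**Working it through.** The plan states no expected rate, sample-size calculation or margin that bears on this point, so there is no figure to reproduce. The check sets the passages side by side.

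**Step 1. Collection against attribution.** Section 4.5 has four collection headings: procedure, device, access site, fistula. Section 4.5.1 and the grid have two attribution targets: device and procedure. The additional question in 4.5.1 concerns a part of the procedure and adds no fistula or access-site category.

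**Step 2. Which events each planned safety result can contain.**

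| Safety result in Section 3.3 | Selects on | Counts fistula or access-site events as such? | Counts serious events scored unrelated? |
|---|---|---|---|
| Safety endpoint | Device | No | No |
| Exploratory, serious procedure-related | Procedure | No | No |
| Exploratory, serious device-related | Device | No | No |
| Exploratory, infections | Device and/or procedure | No | No |

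None of the four results covers fistula or access-site events as such, and none covers all serious events. Section 5 adds only general descriptive summaries. The investigator reporting table in Section 6.4.1 names serious and unanticipated device effects, not serious events scored unrelated.

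**Step 3. Whether such an event can be scored no.** Probable applies when the timing is reasonable and involvement cannot be ruled out, even if other causes are possible. Not Related applies when other factors, such as underlying disease or concurrent treatment, can explain the event. These two can overlap.

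- *Needle infiltration injury.* Its stated cause is cannulation, which happens after the index procedure as part of dialysis. It plainly concerns the fistula, and it is readily explained by concurrent treatment. This is the clearest case.
- *Heart failure from fistula flow.* Section 2.2 gives the fistula as the cause. In a patient with kidney failure, underlying disease is also an available explanation, so both Probable and Not Related can be argued.
- *Steal and arm swelling.* Early on, most investigators would probably score these as related. Nothing in 4.5.1 tells them that the created fistula counts as part of the procedure.

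**Step 4. Whether another endpoint would show the event.** The re-intervention rate covers interventions for patency only. Primary patency ends at such an intervention or at abandonment, and secondary patency ends at abandonment. Maturation requires freedom from stenosis or thrombosis, unless it is met by two-needle dialysis. Stenosis and thrombosis can therefore surface in these results. Steal, arm swelling, heart failure or infiltration injury that leads neither to a patency intervention nor to abandonment need not surface in the re-intervention or patency results. None of these is a safety result.

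**Step 5. Scale.** Section 3.1 allows up to 50 subjects. One subject whose only serious event is scored unrelated changes a subject-level rate by 1/50 = 2 percentage points at full enrolment, and by more if fewer are enrolled. How many such subjects to expect cannot be derived from the documents.

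**The case against.** The strongest reply is that the plan already points towards counting these harms. Section 2.2 introduces its list as risks of the system and procedure, and steal, venous hypertension and heart failure are on it. Section 4.5.1 describes the index procedure as the one that creates the fistula, so harm from that fistula is naturally a consequence of it. Probable is a wide category, and the created fistula is not among the alternative causes that the definitions list. The separate question about the catheter portion implies that procedure is meant more broadly than catheter handling. Stenosis and thrombosis are also visible in the efficacy endpoints.

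Most of this stands, and it limits the point. Many early fistula harms would probably be counted. It does not close the gap, because an introductory sentence in a risk section is not an attribution rule, and needle infiltration injury is named separately from the list.

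A reader might infer that four collection headings against two attribution targets is a contradiction. It is not. The four headings are a filter on what to record, with knee replacement and hysterectomy as examples of what to leave out, and a filter may be wider than an attribution scheme. Nor can one say that the adverse event form lacks a field for the fistula, since the form is not in the documents. Collection is intact: an event scored unrelated is still classed as an SAE. With no hypothesis tests planned, no test or decision rule is affected.

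**Conclusion.** The point holds as a gap in attribution wording and in planned reporting. A collected serious event that concerns the fistula or access site, once scored no for device and procedure, enters none of the four planned safety rates. Whether it is scored no depends on the investigator's judgement under definitions that overlap.

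A reader might go further and infer that the reported safety rates will be too low. The documents do not support that. They give no rate of serious fistula harm and no indication of how often such harm would be scored unrelated, and the breadth of Probable works in the other direction. The conclusion is that events can be left out, not that they will be.

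It rests on reading Section 3.3 as the full list of planned safety results, and on 4.5.1 and the grid as the full attribution scheme. The improvement is worth making because it is cheap and makes one safety figure independent of attribution.

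**What to change.** 1. Add to Section 3.3 the number and percentage of subjects with at least one collected SAE, whichever of the four collection headings it falls under and regardless of attribution. Show it beside the existing device-related and procedure-related rates, over the same 3 months, and keep those rates as they are.
2. State in Section 4.5.1 that events caused by the created endoAVF or its access site count as procedure-related, or else record them under a separate attribution with the same yes/no scale.

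The first change uses data already collected. The cost is one extra table row, a sentence in 4.5.1 (or one more attribution item if the second option is chosen), and a safety figure that may be less favourable. The all-SAE row will also include some events that have little to do with the device, which is why it should stand next to the attributed rates and not replace them.
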